9 ETHICAL CONSIDERATIONS

9.1 Ethical Committee Approval and Informed Consent

The Ethics Review Committee at the University of Göteborg approved the pilot study (Diarie no 13-138). Application for the main study was sent to The Ethics Review Committee as of November 14, 2014. All men randomized to screening will be invited by mail. The invitation contains detailed information about the study, its design, benefits and risks, contact details and a reference to our website with a link to the Swedish National Board of Health and Welfare's written information about PSA testing and its pros and cons. Hence, men who show up for PSA testing are assumed to have read the information provided in the invitation letter and thus make an active choice to participate. Taking a PSA test, as well as undergoing MRI and prostate biopsy tissue sampling, is considered standard clinical practice by the Swedish ethical committees. All men who show up for prostate biopsies at the urology clinic will fill out a standardized health form, which is also used in clinical practice. Here, the patient must check a box "Are we allowed to store your samples in a bio bank? yes/no."

Separate information about a side study of biomarkers and genetics will be administered. Individuals, who want to participate in this study, will have to sign a separate informed consent at the urology clinic

9.2 Subject Confidentiality

Data integration will ensure privacy of human subjects. For data analysis, data will be re-coded for anonymity. Full access to the database will be held by Chief investigator ([name]), data manager ([name]), and study nurse ([name]). All inquiries for data analysis must be approved by the chief investigator prior to data extraction and only anonymized data will be used in analyses.

9.3 Harms, benefits and equipoise

This study aims to evaluate whether a new screening algorithm can improve on the ratio of harms to benefits resulting in that benefits will outweigh the harms.

9.3.1 Potential risks for study participants

Information on potential risks associated with the screening procedures will be mailed to the participants together with the invitation letter. The questions in the questionnaire are of private nature and may evoke feelings of discomfort. If the men experience discomfort upon completion of the questionnaire, they have the possibility to contact a study nurse.

Screening for prostate cancer

Potential risks include anxiety, over-diagnosis, side-effects from biopsies and treatment and negative impact on quality of life but also the risk of delaying diagnosis in men with aggressive cancer. The test interval in this study is longer compared to what is recommended in national and international guidelines. Participating in a screening study like this may give men a false security.

The main downside with PSA testing is the risk of over-diagnosis and subsequent overtreatment of a disease that would otherwise not have caused symptoms or death during the lifespan of a typical man. Such slow-growing cancers do however not have to be treated immediately, but can be monitored (active surveillance). Treatment for localized prostate cancer can lead to impaired erectile function. Radiation is associated with a minor risk of proctitis and urinary urgency, while surgery leads to bothersome urinary leakage in <5%.

Another important ethical aspect regarding prostate cancer screening is that the balance between benefits and harm may vary between individuals, and that the benefit for some men may be significantly less than the potential risks of over-diagnosis of harmless tumors, especially in older men with other co-morbidities, as well as the risks of side effects of treatment in the form of impotence and urinary incontinence. By informing men of the pros and cons of PSA testing and its consequences upstream, i.e., before screening takes place this allows the individual to make an active choice to participate.

To review the risks with both over-diagnosis and delayed diagnosis a close follow-up is planned. See also 8.3

Blood test

Potential risks include anxiety, bruising, and vaso-vagal reactions.

MRI

Potential risks include anxiety, claustrophobia, noise, immobilization for 30-45 minutes. Contraindications are asked for before MRI including: metal implants, pacemaker, kidney failure, contrast medium hypersensitivity.

Low risk gadolinium contrast medium (Dotarem) will be utilized. Plasma-creatinin will be measured for all men undergoing MRI. Height and weight will be measured and eGFR

calculated (kidney function). An eGFR <45 ml/min is an absolute contraindication to MRI in the study. Use of contrast-medium at MRI was discontinued in 2019 except for those who were invited in for their first time. After completion of screening round 1 in 2021 no contrast medium has been given.

Prostate biopsies

Potential risks include discomfort, pain, blood in urine, blood in semen, blood in stool, urinary tract infection, fever and sepsis. Men are informed about these risks at biopsy and given instructions what to do and information who to call in the event of an adverse event.

Survey

The surveys may cause some degree of distress in certain subjects. Questionnaires of various kinds have been carried out for a long time and several of the forms are previously tested on several individuals and have been perceived as easy to understand and can be completed in a short time and without stress.

9.3.2 Potential benefits for study participants

Screening for prostate cancer

Potential benefits include early detection and treatment of prostate cancer at a curable stage, prevention of metastatic disease, morbidity, and disease-specific death.

If the hypothesis is proven to be true, that PSA+MRI reduces the risk of finding insignificant tumors, the major problem with over-diagnosis will be diminished. The number of men who need to be biopsied will be reduced and hence the negative consequences of PSA testing. Most likely, targeted biopsies, guided by MRI findings, will increase the likelihood that a significant cancer is found. Lowering the PSA threshold may enable more men to have their cancer detected at a curable stage. In our previous study (Göteborg-1), regular PSA-testing decreased prostate cancer mortality by 44% and the present study is likely to further reduce mortality from prostate cancer through detection of significant tumors and effective treatment at a curable stage and reduced over-diagnosis.

9.4 Benefit: Risk Endpoints

9.4.1 Exit Examination Analysis

An ordinal overall clinical response will be used, on the individual level, as suggested by Chuang-Stein (Chuang-Stein, 1994).

	Efficacy (no over-diagnosis)	No efficacy (over-diagnosis)
No serious side-effects from screening procedures	Category 1	Category 3
Serious side-effects from screening procedures	Category 2	Category 4

Side-effect leading to withdrawal	Category 5
-----------------------------------	------------

Clinical outcomes

Efficacy: no detection of insignificant disease (no over-diagnosis).

No efficacy: detection of insignificant disease (over-diagnosis).

Toxicity: The following toxicity will be recorded

- Non-serious side-effects from MRI: Contrast medium hypersensitivity requiring medication
- Serious side-effects from MRI: Any major side-effect from MRI requiring hospitalization or causing death
- Non-serious side-effects from Biopsy. Profuse bleeding or infection or pain needing medical attention.
- Serious side-effects from Biopsy: Any major side-effect requiring hospitalization or causing death.

- QoL: reduced HRQoL during screening process (patient-reported outcome assessed by questionnaires)

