8.3 Adverse Event Reporting

Adverse events (see toxicity) from MRI and TRUS biopsy will be recorded continuously and summarized once a year. This summary will be discussed within the study board and possibly together with the Advisory board. The study protocol follows principally clinical recommendations from the Swedish Board of Health and Welfare. One critical point in this study is a potential risk to delay diagnosis of serious cancer when omitting biopsy in men with a negative MRI (and a PSA < 10) in Arm 2 and 3. Therefore, analysis of the incidence of interval cancers in these men is planned as well as studying the characteristics of cancers detected at follow-up screens in men with elevated PSA and negative MRI in previous screening rounds. These data will be presented to the Advisory Board for recommendations. No other stopping rules are specified within the protocol.

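### The benefit-risk score in Protocol 9.4.1 cannot respond to significant cancer, found or missed, and the interval-cancer analysis in 8.3 names no arm 1 comparator

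*Protocol*

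**What the plan says.** Section 9.4.1, under the heading for benefit-risk endpoints, states: "An ordinal overall clinical response will be used, on the individual level". The categories come from two yes/no axes.

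- **Efficacy axis:** "Efficacy: no detection of insignificant disease (no over-diagnosis" on one side and "No efficacy: detection of insignificant disease (over-diagnosis" on the other.
- **Side-effect axis:** the better row is labelled "No serious side-effects from screening procedures". The toxicity list covers MRI and biopsy events, for example "Serious side-effects from Biopsy: Any major side-effect requiring hospitalization or causing death", with quality of life beside them.
- **Category 5:** "Side-effect leading to withdrawal".

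Section 8.3 describes as a critical point "a potential risk to delay diagnosis of serious cancer when omitting biopsy in men with a negative MRI", referring to men in arms 2 and 3 with PSA below 10. It continues that "analysis of the incidence of interval cancers in these men is planned". It also plans to study the cancers found at follow-up screens in men with an earlier elevated PSA and negative MRI, and to put these data before the Advisory Board. Section 9.3.1 lists delayed diagnosis of aggressive cancer among the risks. Section 9.3.2 lists finding cancer while it is curable among the benefits. Section 9.3 says that the study is to judge whether the balance of harms and benefits improves.

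**The concern.** A benefit-risk score should move when either the main benefit or the main risk moves. This one moves with over-diagnosis, serious procedural side-effects and withdrawal. It does not move when a significant cancer is found early, and it does not move when one is missed. Reading the category numbers from best to worst, a man whose significant cancer was missed after a negative MRI ranks ahead of a man with a detected Gleason 6 cancer.

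The experimental strategy works by doing fewer biopsies, so the trade-off of interest is fewer insignificant cancers against possibly later diagnosis of significant ones. A shift towards Category 1 could be reported as net benefit when only one side of that trade-off had been weighed. The analysis in 8.3 that looks at the other side has no stated reference group. An interval-cancer rate in MRI-negative men of arms 2 and 3 alone does not show whether it exceeds what follows a systematic-biopsy work-up.

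**Working it through.** **1. The plan's own rates.** Section 6.1 assumes insignificant cancer in 9% of arm 1 men with PSA ≥ 3 and a 50% reduction, so 0.09 × (1 − 0.50) = 0.045 in arms 2+3. With 1:2 allocation (1:1:1 in section 3.5), 80% power, two-sided 5% and a continuity correction, the two-proportion formula gives 382 + 764 = 1,146. The stated figure is 1,164, so the result is (1,164 − 1,146)/1,164 = 1.5% lower. Without the correction it is 1,050. Onward, 1,164/0.07/0.50 = 33,257, against 33,260 stated. The plan's figures are consistent with 9% and 4.5%.

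**2. Sorting outcomes by the 9.4.1 table** (no serious side-effect, no withdrawal):

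| Man's outcome | Insignificant disease detected? | Category |
|---|---|---|
| No cancer | No | 1 |
| Significant cancer detected | No | 1 |
| Significant cancer missed | No | 1 |
| Insignificant cancer detected | Yes | 3 |

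The first three rows cannot be told apart. With a serious side-effect they all move to Category 2, and with withdrawal for a side-effect to Category 5. Under section 4.1, most MRI-negative men in arms 2 and 3 are not biopsied and so cannot have a biopsy side-effect. Category 1 is their usual result.

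**3. Sensitivity of the score to missed cancers.** Take 1,000 men with PSA ≥ 3 in each group and set side-effects aside.

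- Efficacy column, arm 1: 1,000 × (1 − 0.09) = 910.
- Efficacy column, arms 2+3: 1,000 × (1 − 0.045) = 955.
- Missed significant cancers in arms 2+3: 1,000 × S × m, where S is the prevalence and m the share missed. The documents give neither. Assume S from 10% to 20% and let m run over its whole range.

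| S (assumed) | m = 0% | m = 10% | m = 50% | m = 100% | Efficacy, arm 1 vs arms 2+3 |
|---|---|---|---|---|---|
| 10% | 0 | 10 | 50 | 100 | 910 vs 955 |
| 15% | 0 | 15 | 75 | 150 | 910 vs 955 |
| 20% | 0 | 20 | 100 | 200 | 910 vs 955 |

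The body of the table is missed cancers per 1,000 men. Neither S nor m appears in the efficacy formula, so the last column is constant for any values chosen.

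**4. Coverage of 8.3.** The interval-cancer analysis is tied to MRI-negative men in arms 2 and 3. Arm 1 is not named. Men in arms 2 and 3 with a positive MRI and benign targeted biopsies are not in the group either, although many of them also have no systematic biopsy under section 4.1.

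**The case against.** The strongest reply is that the protocol examines significant cancer properly elsewhere, and that 9.4.1 carries little weight. Most of this stands.

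- Section 9.4.1 sits in the ethics chapter. It is not among the objectives, in the outcome table of 2.5 or in the analysis plan of 6.2, and it has no test or decision rule. Section 6.2.3 bases the main conclusion on significant versus insignificant cancer. This limits the weight of the point, but 9.4.1 still says that the score will be used and fixes its content, so it is not a detail left to an analysis plan.
- A reader might infer that delayed diagnosis is studied only in 8.3. It is not. Sections 2.2 and 6.2.2 compare detection of significant cancer by arm, without a test. Sections 2.5 and 3 repeat the comparison as arm 1 versus arm 2 over later rounds, and section 3 plans comparisons of biopsy strategies within arm 1. None of this feeds the 9.4.1 score.
- A reader might infer that the score must favour the arm with fewer biopsies. The side-effect axis and Category 5 can work the other way, for example through the second biopsy session recommended in 4.1 for arm 2 and 3 men with cancer on targeted biopsy.
- A reader might infer that untested men would score as successes. Allocation to an arm happens only when a PSA result arrives (section 3.5), so the arms contain no untested men.
- It is tempting to express missed cancers as a share of the fall in insignificant ones. The documents give no prevalence or miss rate. The ratio would also set a gross count in arms 2+3 against a between-arm difference, although arm 1 work-ups can miss cancers too.
- Ranking a later cancer below over-diagnosis is a value judgement. A cancer found at the next round may be new, and its detection depends on arm, because under 4.1 arm 1 men with PSA ≥ 3 are biopsied again while most MRI-negative men in arms 2 and 3 are not. This stands and shapes the fix.

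**Conclusion.** The point holds in a limited form. The 9.4.1 score cannot respond to significant-cancer outcomes. At the plan's 9% and 4.5%, side-effects aside, its efficacy column is 910 versus 955 per 1,000 men with PSA ≥ 3 at any miss rate. That result needs only the protocol's definitions and planned rates. The assumed prevalence merely illustrates how many missed cancers (0 to 200 per 1,000) the score could pass over.

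The defect lies in 9.4.1 and in the missing arm 1 comparator in 8.3. It does not touch the primary analysis, the sample size or the secondary comparison of significant cancer. The documents do not show that the experimental arms miss more significant cancers, nor that the score is bound to favour them. It should be corrected, because a score presented as benefit against risk leaves out a benefit and a risk that the protocol itself names.

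**What to change.** 1. In 8.3, report interval significant cancers by randomised arm among all men with PSA ≥ 3, with arm 1 as comparator, from the 3-monthly registry linkage in section 5.1. For round 1 this group is defined by the PSA result that triggers allocation, before the work-ups diverge, so the comparison keeps the randomisation.
2. In 9.4.1, stop counting an interval significant cancer after a negative work-up as efficacy. Tabulate each category by significant-cancer status (none, detected, interval) and impose no rank of interval cancer against over-diagnosis.
3. Show cancers detected at the next screening round separately, with a note that repeat biopsy differs by arm.
4. State that 9.4.1 otherwise covers only over-diagnosis and procedural harm, and must be read together with 6.2.2 and 8.3.

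The cost is rewording plus a status variable derived from data already linked. No sample-size figure changes. There are two downsides. Classification is complete only once the screening interval has passed, generally 2 years for men with PSA ≥ 1.2 and 4 years after two successive negative work-ups (section 4.2). And because section 9.3.1 records round 1 as completed in 2021, the change must be dated and labelled as made after round 1.

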10 PUBLICATION OF RESEARCH FINDINGS

The results of the study and sub-studies will be reported as standard scientific manuscripts in peer-reviewed medical journals.

Comments in the end:

The study population will be identified from a random sample from the population register of men in the age group 50-60 years in the county of Göteborg and six surrounding municipalities, and as such, be truly population-based and generalizable to the entire male population of this age. Since randomization to screening versus control is performed upfront and without informed consent, this allows evaluating the effectiveness of screening on prostate-cancer mortality and to more accurately estimate this effect if population-based screening were introduced. This is in contrast to if the study had been designed as an efficacy trial with informed consent prior to randomization, which may instead introduce healthy screenee bias. The current design will minimize this bias, although it is known from Göteborg-1 that non-attendees to screening have a higher risk of prostate cancer mortality, than attendees (Bergdahl 2009)

A limitation of the study is that the vast majority of Swedes in this age group are Caucasians. However, there was no predefined selection per ethnicity. Nevertheless, the results of the study may not be generalizable to non-caucasian populations.

REFERENCES

